14.1. Participant Accrual

Participants of both genders, from all racial and ethnic groups are eligible for this trial if they meet the criteria outlined in Section 3.0. To date, there is no information that suggests differences in drug metabolism or disease response among racial or ethnic groups or between the genders, indicating that results of the trial will be applicable to all groups. Efforts will be made to extend the accrual to a representative population, but in a phase II study with limited accrual, a balance must be struck between patient safety considerations and limitations on the number of individuals exposed to potentially toxic or ineffective treatments on the one hand, and the need to explore gender, racial, and ethnic aspects of clinical research on the other. If differences in outcome that

correlate to gender, age, racial, or ethnic identity are noted, accrual may be expanded, or additional studies may be performed to investigate those differences more fully.

14.2. Sample Size

Target is 20 patients for 16 evaluable participants.

To allow for 25% unevaluable participants, a maximum of up to 20 participants will be enrolled. We anticipate enrollment to be completed in 36 months with primary outcome measure defined in 12 months. The sample size for this trial is based on 3 primary factors: safety based on risk versus benefit. Sample size estimates were based on a single stage phase II clinical trial with the goal of demonstrating that the objective response rate of poly-ICLC is better than an objective response rate of a *poor* drug. For the sample size calculation, we assumed that the response rate of a poor drug (P_0) was 5% (i.e., $P_0 = 5\%$) and that the objective response rate poly-ICLC (P) would be at least 25% (i.e., $P = 25\%$).

In addition, the type I error rate (alpha) was set to 0.05 (5%) and the type II error rate ($\beta = 1 - \text{power}$) was set to 0.20 (20%). Using a single stage design, a sample size of 16 participants achieves at least 80% power to demonstrate that the objective response rate of poly-ICLC is better than a poor objective response rate of 5% and at least 25%. If the number of responders is 3 or more, the hypothesis that $P \leq 5\%$ is rejected with an actual error rate of 0.043. If the number of responses is 2 or less, the hypothesis that $P \geq 25\%$ is rejected with an actual error rate of 0.197. Sample size estimates were determined using PASS v. 19.0.2 (NCSS, LLC, Kaysville, UT).

Table 15: PASS Output Single-Stage Phase II Clinical Trials Analysis

Design for Testing $H_0: P \leq P_0$ versus $H_1: P \geq P_1$							
P_0	P_1	Alpha	Beta	Cut-Off $R + 1$	N	Actual Alpha	Actual Beta
0.05	0.25	0.050	0.2	3	16	0.04	0.197
Report Definitions							

P_0 is the maximum response proportion of a poor drug.P_1 is the minimum response proportion of a good drug.N is the sample size.If the number of responses $\geq R+1$, P_0 is rejected.If the number of responses $\leq R$, P_1 is rejected.Alpha is the probability of rejecting that $P \leq P_0$ when this is true.Beta is the probability of rejecting that $P \geq P_1$ when this is true.							

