Endpoints:	Primary endpoint 
Objective response rate (CR+PR) within the first 48 weeks (12 cycles) of therapy, using RAPNO criteria Secondary endpoints: 
PFS at 12, 24 and 60 monthsBest response rate (CR+PR) within 24 cycles of therapyClinical benefit response rate (CR+PR+MR+SD) after 12 and 24 cycles of therapyPoly-ICLC-related toxicities Exploratory endpoints 
Vision response after 12 and 24 cycles of therapy defined as 0.2 logMAR or greater in acuity improvementPatient reported outcomes and quality of life measuresBiological correlatesComparison of RANO and RAPNO response determinations
Accrual Objectives:	Up to 20 participants will be enrolled to obtain a minimum of 16 evaluable participants on this study.
Study Duration:	Participants will be followed for a minimum of 5 years from treatment. Overall survival outcomes will continue to be measured up to 5 years from treatment.
Interim Analysis:	There will not be an interim analysis for efficacy.

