14. STATISTICAL CONSIDERATIONS

Primary Endpoints

The primary endpoint of the study is objective response rate (defined as CR or PR) during the first 12 months of treatment. Response will be assessed through the time of the post-12th cycle tumor assessment, or through the last tumor assessment time during this nominal period for patients in follow-up but who have withdrawn from protocol therapy, or through the last available tumor assessment for patients who are lost to follow-up during this time.

The percent change in tumor sizes compared to baseline will be recorded at each evaluation time and will be used to define the categorical response as described below, per the definition of CR, PR, MR, SD, and PD in section 10.4.

- For tumors that regress compared to baseline during the assessment period without first satisfying the criteria for progressive disease (PD), response will be defined at the nadir of the tumor size compared to baseline provided that the percent reduction at the nadir satisfies the definition of CR, PR, or MR per section 10, with the response value of CR, PR, or MR determined by the percent reduction at this time.

The associated time of response will also be recorded.

- For tumors that progress compared to baseline and satisfy the definition of PD without first satisfying the criterion at least for minor response (MR), response will be defined at the first time at which the percent increase in tumor size compared to baseline satisfies the criterion for PD. The response value will be PD. The associated time of response will also be recorded. Progressive disease could be confirmed with a short follow-up MRI (+/- 6 weeks) per treating physician decision, otherwise continue with MRI interval per protocol.
- For tumors that neither regress sufficiently to satisfy the criterion for MR nor progress sufficiently to satisfy the criterion for PD during the assessment period, the response value will be determined to be SD.

Patients will be considered evaluable for response if they have received at least one dose of treatment and have at least one post-baseline tumor assessment.

Patients who undergo gross total resection while on study will be excluded from further response at the time of surgery. Patients who have measurable residual disease (at least twice the thickness of the MRI slide) after resection will be able to continue study drug and the post-op MRI will be used as the new baseline.

Secondary Endpoints

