14.3. Statistical Analysis Plan

The primary goal of the study is to evaluate the effectiveness of the poly-ICLC. Based on the single stage design, response of the drug will be determined after 16 participants are evaluable for the primary endpoint assessment. Participants will be classified based on response (CR/PR vs. MR/SD/PD). If at least 3 of 16 participants respond to treatment, the hypothesis that $P \leq 5\%$ is rejected at alpha = 0.05 and accept that the higher rate of P greater or equal to 25% is more likely; otherwise, the drug will be deemed ineffective based on having an objective response rate

not significantly different than the objective response rate of a poor drug. Comparison between RANO and RAPNO response criteria will be descriptive only.

Key secondary outcomes will be examined at baseline including clinical, quality of life and visual function. Following complete accrual, study enrollment and completion will be summarized as per a Consort Diagram with reasons for withdrawal or unable to complete the study. Appropriate data analysis sets will be defined as follows. The full-analysis set will include data from all participants who receive ≥ 1 dose of therapy on this study; a safety analysis set will comprise data from participants in the full-analysis set with any treatment doses. Other data sets (responding, evaluable) will be defined and will include data from participants who have the necessary baseline and on-study measurements to provide interpretable results for specific parameters of interest.

Descriptive summaries will be prepared to show sample size, mean, standard deviation, 95% confidence intervals (CIs) median, minimum, and maximum for continuous variables and counts, percentages, and 95% CIs for categorical variables.

For endpoints relating to tumor control, participant well-being, and biomarkers, analyses will be done based on the full analysis, responding, evaluable data sets, as appropriate. Time-to-event analyses will be performed with reference to the date of first treatment on this study. Analyses will focus on evaluation of outcomes and will be largely descriptive. Changes in tumor volumes will be summarized by medians, ranges, and the corresponding 95% CI.

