Based on the safety analysis set, information regarding study treatment administration, drug dosing and cycle compliance, safety variables, will be described and summarized. Data from the biological analysis will also be described and summarized. Safety will be assessed via tabulations of AEs and SAEs as well as Diary recordings following treatment dose/cycle of therapy.

All analyses for outcome results will be based on evaluable participants, as defined in section 14.

At the end of the trial, we will report poor performance if the treatment is rejected when not meeting the criteria of at least 3 responders' cases. If there is no success, we will report a failure to reject the null hypothesis. If the null hypothesis is rejected, the probability of the estimated success rate will be reported and 95% confidence intervals as well as the distribution of changes in tumor size.

Dose-limiting toxicity (DLT) is not an objective in this trial. Toxicity will be continuously monitored.

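### Enrolling 20 to obtain 16 evaluable allows for 20% unevaluable, not the stated 25%; at a 25% loss 15 are expected and the 3-responder rule has 76.4% power rather than 80.3%.

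*Combined protocol and SAP*

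**What the plan says.** Section 14.2 opens with "Target is 20 patients for 16 evaluable participants" and continues: "To allow for 25% unevaluable participants, a maximum of up to 20 participants will be enrolled". The Protocol Summary agrees on the two counts: "Up to 20 participants will be enrolled to obtain a minimum of 16 evaluable participants on this study".

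The design is a single-stage test of a 5% null response rate against 25%. For it, section 14.2 states that "a sample size of 16 participants achieves at least 80% power". The null is rejected at 3 or more responders, with actual error rates of 0.043 (type I) and 0.197 (type II).

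Section 14.3 ties the decision to the same number: "response of the drug will be determined after 16 participants are evaluable for the primary endpoint assessment". It gives the criterion as at least 3 of 16. On final reporting it says that "we will report poor performance if the treatment is rejected when not meeting the criteria of at least 3" responders, this time without repeating the denominator.

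Under section 14, Primary Endpoints, participants are evaluable if they "have received at least one dose of treatment and have at least one post-baseline tumor assessment".

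**The concern.** The three figures 20 enrolled, 16 evaluable and 25% unevaluable cannot all be true. The counts 20 and 16 recur consistently in the Protocol Summary and in sections 14.2 and 14.3, so the percentage is the figure that does not fit.

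This matters because the allowance is what protects the power statement. If a quarter of those enrolled were unevaluable, the expected evaluable number would be one short of the 16 on which the power statement, Table 15 and the 3-of-16 rule rest. The plan has no fallback for that case. Twenty is a maximum and there is no replacement rule. Section 14.1 allows accrual to be expanded only if outcome differences by gender, age, race or ethnicity are noted. No decision rule or error rates are given for fewer than 16 evaluable.

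**Working it through.** **Inputs**, all from section 14.2: null rate 0.05; target rate 0.25; nominal alpha 0.05; cut-off 3 responders; 16 evaluable; 20 enrolled; stated unevaluable share 25%.

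**1. Reproduce the plan's design at 16 evaluable.** With X ~ Bin(16, p), reject if X ≥ 3.

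- Type II error = P(X ≤ 2 | 0.25) = 0.75^16 + 16(0.25)(0.75^15) + 120(0.25²)(0.75^14) = 0.0100 + 0.0535 + 0.1336 = 0.197. Power = 0.803.
- Type I error = 1 − P(X ≤ 2 | 0.05) = 1 − (0.4401 + 0.3706 + 0.1463) = 0.043.

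Both match the plan.

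**2. Check the allowance.**

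- Share of those enrolled who may be unevaluable: (20 − 16)/20 = 0.20.
- Excess relative to the evaluable target: (20 − 16)/16 = 0.25.
- Enrolment needed for a 25% loss: 16/(1 − 0.25) = 21.3, so 22.
- Enrolment needed for a 20% loss: 16/(1 − 0.20) = 20.

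The stated 20 follows from 25% only as 16 × 1.25 = 20, that is, by multiplying the target by 1 + d where dividing by 1 − d is required.

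**3. Consequence at the stated 25%.** Expected evaluable = 20 × 0.75 = 15. With the cut-off still at 3:

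- Type II error = 0.75^15 + 15(0.25)(0.75^14) + 105(0.25²)(0.75^13) = 0.0134 + 0.0668 + 0.1559 = 0.236. Power = 0.764.
- Type I error = 1 − (0.4633 + 0.3658 + 0.1348) = 0.036.

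| Evaluable | Power | Type II error | Type I error |
|---|---|---|---|
| 16 | 0.803 | 0.197 | 0.043 |
| 15 | 0.764 | 0.236 | 0.036 |

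Difference in power: 0.8029 − 0.7639 = 0.039.

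**4. Chance of reaching 16.** This step assumes, beyond what the documents say, that each of 20 participants is unevaluable independently with the same probability. Then P(at least 16 evaluable) = P(Bin(20, 0.75) ≥ 16) = 0.415 at a 25% loss and P(Bin(20, 0.80) ≥ 16) = 0.630 at 20%.

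**The case against.** The strongest reply is that the 25% is only 4/16 with the wrong label. On that view the sponsor never expected to lose a quarter of those enrolled, no operative rule uses the percentage, and no power is lost. The cap, the target, the cut-off, Table 15 and the 16-evaluable trigger all agree, and the power statement is made explicitly for 16 participants.

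Most of that stands as a limit on the size of the problem. The 76.4% is conditional on a 25% loss, and the documents give no observed rate of unevaluability. The definition of evaluable is also lenient: one dose and one post-baseline scan. Section 5.3 requires an MRI at completion of therapy or relapse, and section 5.4 continues imaging off therapy, so a participant who stops before the scheduled scan at the end of cycle 3 may still count. Losses may therefore be well below 25%.

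It does not rescue the sentence. The wording describes a share of participants who are unevaluable, those participants are not among the 16, and nowhere is the allowance expressed relative to the evaluable number.

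Two further points are fair. First, the missing denominator in the final reporting rule carries little weight, because the same section has already stated the criterion as 3 of 16. Second, error rates for 15 evaluable show one side only. The Protocol Summary sets 16 as a minimum, and if the cut-off of 3 were applied to more evaluable participants, the exact type I error would be 0.0503 at 17 and 0.0755 at 20.

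**Conclusion.** The point holds. The cap allows for 20% unevaluable, so section 14.2 claims a margin that the design does not have. At the stated 25%, one fewer evaluable participant is expected than the design needs, and power with the cut-off of 3 falls from 80.3% to 76.4%, below the stated minimum of 80%. Type I error falls from 0.043 to 0.036, so there is no inflation in that direction.

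The percentage error is exact and needs no assumption. The power loss depends on 25% of those enrolled being unevaluable and on the cut-off staying at 3. The chances of reaching 16 evaluable depend in addition on independent losses. The calculation for 16 evaluable is sound, so this is a correction to the sample-size justification and does not invalidate the design.

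**What to change.** In section 14.2, replace the 25% with *20% unevaluable (4 of 20)* and add one sentence: *If only 15 participants are evaluable, the cut-off of 3 responders has power of about 76% and a type I error of about 0.036.* Enrolment, the cut-off, Table 15, the Protocol Summary and section 14.3 stay as they are.

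The cost is one corrected percentage and one sentence; the stated allowance becomes slightly less favourable.

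The sponsor should confirm that 20% is the loss it is prepared to plan for. If it expects 25% of those enrolled to be unevaluable, the consistent alternative is a cap of 22, which costs two more participants and requires the Protocol Summary to change as well. It would also help to say in the same place that the test uses 16 evaluable participants, or to give the rule if more than 16 are evaluable.

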14.3. Statistical Analysis Plan

The primary goal of the study is to evaluate the effectiveness of the poly-ICLC. Based on the single stage design, response of the drug will be determined after 16 participants are evaluable for the primary endpoint assessment. Participants will be classified based on response (CR/PR vs. MR/SD/PD). If at least 3 of 16 participants respond to treatment, the hypothesis that $P \leq 5\%$ is rejected at alpha = 0.05 and accept that the higher rate of P greater or equal to 25% is more likely; otherwise, the drug will be deemed ineffective based on having an objective response rate

not significantly different than the objective response rate of a poor drug. Comparison between RANO and RAPNO response criteria will be descriptive only.

Key secondary outcomes will be examined at baseline including clinical, quality of life and visual function. Following complete accrual, study enrollment and completion will be summarized as per a Consort Diagram with reasons for withdrawal or unable to complete the study. Appropriate data analysis sets will be defined as follows. The full-analysis set will include data from all participants who receive ≥ 1 dose of therapy on this study; a safety analysis set will comprise data from participants in the full-analysis set with any treatment doses. Other data sets (responding, evaluable) will be defined and will include data from participants who have the necessary baseline and on-study measurements to provide interpretable results for specific parameters of interest.

Descriptive summaries will be prepared to show sample size, mean, standard deviation, 95% confidence intervals (CIs) median, minimum, and maximum for continuous variables and counts, percentages, and 95% CIs for categorical variables.

For endpoints relating to tumor control, participant well-being, and biomarkers, analyses will be done based on the full analysis, responding, evaluable data sets, as appropriate. Time-to-event analyses will be performed with reference to the date of first treatment on this study. Analyses will focus on evaluation of outcomes and will be largely descriptive. Changes in tumor volumes will be summarized by medians, ranges, and the corresponding 95% CI.

Based on the safety analysis set, information regarding study treatment administration, drug dosing and cycle compliance, safety variables, will be described and summarized. Data from the biological analysis will also be described and summarized. Safety will be assessed via tabulations of AEs and SAEs as well as Diary recordings following treatment dose/cycle of therapy.

All analyses for outcome results will be based on evaluable participants, as defined in section 14.

At the end of the trial, we will report poor performance if the treatment is rejected when not meeting the criteria of at least 3 responders' cases. If there is no success, we will report a failure to reject the null hypothesis. If the null hypothesis is rejected, the probability of the estimated success rate will be reported and 95% confidence intervals as well as the distribution of changes in tumor size.

Dose-limiting toxicity (DLT) is not an objective in this trial. Toxicity will be continuously monitored.

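### The 80% power is for rejecting an ORR of 5% or less when the true ORR is 25%; it does not let 3 of 16 responders support an ORR of at least 25%, as sections 14.2 and 14.3 word it.

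*Combined protocol and SAP*

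**What the plan says.** Section 14.2 (Sample Size) sets a poor-drug rate P0 of 5% and assumes a rate for poly-ICLC: "and that the objective response rate poly-ICLC (P) would be at least 25" percent. Alpha is 0.05 and beta 0.20. The power statement is that "a sample size of 16 participants achieves at least 80% power to demonstrate that the objective response rate of poly-ICLC is better than" the poor rate, and the sentence ends "better than a poor objective response rate of 5% and at least 25" percent. The section then gives the decision rule: 3 or more responders reject P ≤ 5% (actual error 0.043), and 2 or fewer reject P ≥ 25% (actual error 0.197). Table 15 repeats the design with H0: P ≤ P0 and H1: P ≥ P1. Its definitions say that reaching the cut-off rejects P0; they do not say that P1 is then accepted.

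Section 14.3 (Statistical Analysis Plan) states the conclusion to be drawn. "If at least 3 of 16 participants respond to treatment", the hypothesis P ≤ 5% is rejected at alpha 0.05 and the investigators "accept that the higher rate of P greater or equal to 25% is more likely". Later in the same section, if the null is rejected, the estimated success rate is to be reported with 95% confidence intervals and the distribution of tumor size changes.

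**The concern.** A single-arm design of this kind has one null hypothesis, here P ≤ 5%. The 25% is the planning rate at which power is evaluated. Crossing the cut-off rejects the null. It says nothing direct about whether the rate reaches 25%, because every rate between 5% and 25% is also compatible with rejection. Section 14.2 presents the 80% as power to demonstrate both that the rate exceeds 5% and that it is at least 25%. Section 14.3 carries the second part into the pre-specified conclusion. The smallest successful result, 3/16, is itself below 25%.

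At stake is what this uncontrolled 16-patient trial may claim on its primary endpoint. Followed literally, a result at the cut-off would be reported as favouring an ORR of 25% or more when the data support only a rate above 5%.

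**Working it through.** **Inputs.** From section 14.2 and Table 15: n = 16, P0 = 0.05, P1 = 0.25, cut-off 3, stated alpha 0.043 (0.04 in Table 15), stated beta 0.197. From section 14.3: success if X ≥ 3. The test is one-sided in effect, because the null is P ≤ 5%.

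**1. Reproduce the plan's figures.** With X ~ Bin(16, p):

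- Alpha = P(X ≥ 3 | 0.05) = 1 − (0.4401 + 0.3706 + 0.1463) = 0.0429. Stated 0.043.
- Beta = P(X ≤ 2 | 0.25) = 0.0100 + 0.0535 + 0.1336 = 0.1971. Stated 0.197.
- Power = 1 − 0.1971 = 0.8029.

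Both agree. The power is by construction P(reject P ≤ 5% | true ORR = 25%).

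**2. What the cut-off result supports.** At X = 3 the observed rate is 3/16 = 18.75%. Exact (Clopper-Pearson) limits:

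- One-sided 95% lower bound: the 0.05 quantile of Beta(3, 14) = 0.0531, or 5.3%.
- Two-sided 95% CI: the 0.025 quantile of Beta(3, 14) to the 0.975 quantile of Beta(4, 13) = 0.04047 to 0.45646, or 4.0% to 45.6%.

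The one-sided bound just clears 5%, in line with the test, and is far below 25%.

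**3. Chance of meeting the rule when the true ORR is below 25%.**

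| True ORR | P(X ≥ 3 of 16) |
|---|---|
| 5% | 0.043 |
| 10% | 0.211 |
| 15% | 0.439 |
| 20% | 0.648 |
| 25% | 0.803 |

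**4. Is P ≥ 25% more likely than not?** This needs a prior, which the plan does not give; I assume two conventional ones. With a uniform prior the posterior after x responders is Beta(x + 1, 17 − x). With a Jeffreys prior it is Beta(x + 0.5, 16.5 − x).

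| Responders | P(ORR ≥ 25%), uniform | P(ORR ≥ 25%), Jeffreys |
|---|---|---|
| 3/16 | 0.35 | 0.29 |
| 4/16 | 0.57 | 0.52 |

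At 3/16 under the uniform prior, P(ORR ≤ 5%) = 0.009, so P(5% < ORR < 25%) = 1 − 0.353 − 0.009 = 0.638. The range the wording leaves out is the one best supported.

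**5. Scale, for illustration only.** The protocol proposes no test of P ≤ 25%. If the same rule were read as one, its type I error at P = 25% would be 0.803. Rejecting P ≤ 25% at one-sided 0.05 would need 8 of 16: P(X ≥ 8 | 0.25) = 0.027, whereas P(X ≥ 7 | 0.25) = 0.080.

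**The case against.** The best defence is that section 14.3 does not claim proof. It rejects 5% and calls the higher rate more likely, which is a comparison within a two-hypothesis design. Taken as exactly 25% against exactly 5%, that is right at the cut-off: the likelihood ratio at 3/16 is (0.25/0.05)³ × (0.75/0.95)¹³ = 125 × 0.0463 ≈ 5.8 in favour of 25%. Section 14.2 also states the narrower goal of beating a poor drug, introduces 25% as an assumption, and gives correct error rates. A reader can recover the true operating characteristics, and the phrase about 25% may be a drafting slip. The planned estimate and interval would show any reader how imprecise the result is.

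Much of this stands. A reader might infer that the plan treats 3/16 as showing an ORR of at least 25%; section 14.3 is softer than that. The posterior argument defeats its wording only at exactly 3/16, since from 4/16 the two priors give 0.57 and 0.52. The pass rates at 10% to 20% belong to the design and would not change with the wording.

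Two things do not stand. Section 14.3 accepts the composite claim P ≥ 25%, not the single point 25%, and so passes over the interval that contains the observed 18.75%. And section 14.2 does use the language of demonstration, with a power figure attached to the 25%. The planned interval helps the reader but leaves the pre-specified conclusion in place beside it.

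**Conclusion.** The concern holds as a misstated power property in section 14.2 and an unsupported conclusion on success in section 14.3. The rule supports an ORR above 5%. At its minimum it rests on an observed 18.75% with a one-sided lower bound of 5.3%, and a drug with a true ORR of 20% would meet it about 65% of the time. These figures are exact binomial results from the protocol's own inputs. Only the posterior probabilities rest on assumed priors, and both priors agree on which side of one half they fall at 3/16 and at 4/16.

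Two stronger inferences are not supported. One is that the trial is mis-sized or its test invalid: the sample size, cut-off, alpha and power are all correct for 5% against 25%. The other is that the wording would drive a wrong decision on further development: the documents reviewed contain no go/no-go rule tied to 25%, and the primary endpoint in the Protocol Summary sets no such threshold. The effect is confined to what the trial is allowed to conclude.

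**What to change.** In section 14.2, replace the power statement with: *16 evaluable participants give at least 80% power to reject ORR ≤ 5% if the true ORR is 25%*, and delete the added claim about reaching 25%.

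In section 14.3, replace the conclusion on success with: *if 3 or more of 16 respond, conclude that the ORR exceeds 5%*, and delete the acceptance of P ≥ 25%. The estimate and 95% CI already planned later in that section then carry the information on how large the rate may be; no new analysis is needed.

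The cost is two sentences of wording and a slightly weaker allowed conclusion. Sample size, cut-off, alpha and power stay as they are.

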- Progression free survival (PFS), defined as the time from start of treatment to the first occurrence of tumor recurrence, tumor progression, occurrence of a second malignancy, or death from any cause. Patients event-free at last follow-up will be censored in analysis. PFS will be determined at 12, 24 and 60 months.
- Objective response rate (defined as CR or PR) after 24 cycles of treatment. Response will be assessed through the time of the post-24th cycle tumor assessment, or through the last tumor assessment time during this nominal period for patients in follow-up, but who have withdrawn from protocol therapy, or through the last available tumor assessment for patients who are lost to follow-up during this time.
- Clinical benefit defined as (CR+PR+MR+SD). Clinical benefit will be assessed through the time of the post-12 and 24th cycle tumor assessment, or through the last tumor assessment time during this nominal period for patients in follow-up but who have withdrawn from protocol therapy, or through the last available tumor assessment for patients who are lost to follow-up during this time.
- The grade and duration of CTCAE toxicities observed during treatment using CTAE version 5.0.
- Evaluation for visual acuity for patients with optic pathways gliomas will be assessed at 12 months and 24 months from starting therapy. Patient visual outcome will be assessed through the time of the post-12th and 24th cycle visual assessment, or through the last visual assessment time during this nominal period for patients in follow-up but who have withdrawn from protocol therapy, or through the last available tumor assessment for patients who are lost to follow-up during this time.

Exploratory Endpoint

The RANO criteria for response assessment will be determined and descriptively compared to the primary response using RAPNO.

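### Read literally, Section 14.3 drops from PFS any treated patient who has an event but is never imaged after baseline, and it conflicts with the plan's own full-analysis set

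*Combined protocol and SAP*

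**What the plan says.** Near its end, Section 14.3 sets one population for every outcome: "All analyses for outcome results will be based on evaluable participants, as defined in section 14". The operative definition is in Section 14 under Primary Endpoints, where patients count as "evaluable for response if they have received at least one dose of treatment and have at least one post-baseline tumor assessment".

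Earlier in Section 14.3 the plan takes a different line. "The full-analysis set will include data from all participants who receive ≥ 1 dose of therapy on this study"; no scan is required. For tumor control, well-being and biomarkers, "analyses will be done based on the full analysis, responding, evaluable data sets, as appropriate". No set is tied to any particular endpoint.

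PFS is the first secondary endpoint in Section 14, "defined as the time from start of treatment to the first occurrence of tumor recurrence, tumor progression, occurrence of a second malignancy, or death"; deaths count whatever their cause. The censoring rule that goes with it reads: "Patients event-free at last follow-up will be censored in analysis". The time points are fixed as well: "PFS will be determined at 12, 24 and 60 months". Section 14.3 confirms the time origin: "Time-to-event analyses will be performed with reference to the date of first treatment on this study".

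**The concern.** PFS runs from the first dose, but under the literal rule a patient enters the analysis only if a later scan exists. The first scheduled scan is at the end of cycle 3, about 12 weeks after the clock starts (Protocol Summary). Entry therefore depends on something that happens after time zero. Some PFS events need no scan: death and second malignancy never do, and Section 10.4 asks for confirmatory imaging of clinical progression only where feasible.

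A patient who dies in week 8 without a scan has had a PFS event under Section 14, and also under the shorter PFS definition in Section 10.5. The closing sentence of Section 14.3 would still leave that patient out. The omitted patients are failures, so the error can only push PFS upward, and a single-arm trial has no comparator in which it could cancel. With two conflicting rules and no set named for PFS, the choice could also be made after results are known.

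**Working it through.** **1. The plan's own figure.** Section 14.2 sizes the trial on response only: 16 evaluable patients, success at 3 or more responders, null rate 5%, target rate 25%. The exact binomial gives

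- P(X ≥ 3 | n = 16, p = 0.05) = 0.0429, stated as 0.043;
- P(X ≤ 2 | n = 16, p = 0.25) = 0.1971, stated as 0.197.

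Both reproduce. The plan states no rate, sample size or power for PFS, so there is no PFS figure to check.

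**2. Who falls in which set.** This applies the definitions in Sections 14 and 14.3, the imaging rules in Sections 5.3, 5.4 and 10.4, and Appendix 3 (note 3).

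| Patient | Full-analysis set | Evaluable set |
|---|---|---|
| Radiographic progression | in | in |
| Clinical progression, imaged at or after progression | in | in |
| Death, second malignancy or clinical progression, never imaged after baseline | in, as an event | out |
| Event-free, never imaged after baseline | in, censored | out |
| Enrolled, never dosed | out | out |

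Only the third row biases PFS materially. The fourth adds little information, and none if the patient is censored at first dose.

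**3. Size.** Inputs:

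- N = 20 treated. Section 14.2 gives 20 as the maximum enrolled; that all are dosed is an assumption.
- f = number of treated patients with an early event and no post-baseline scan, from 0 to 20 − 16 = 4.
- S = 12-month PFS in scanned patients. The documents give no value; 75% is assumed, with 60% to 90% as a range.

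If the f events come before the first scheduled scan and the other patients follow the scanned curve, then

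all-treated PFS ≈ (N − f)/N × S.

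| f | S = 60% | S = 75% | S = 90% |
|---|---|---|---|
| 0 | 60.0% | 75.0% | 90.0% |
| 1 | 57.0% | 71.3% | 85.5% |
| 2 | 54.0% | 67.5% | 81.0% |
| 3 | 51.0% | 63.8% | 76.5% |
| 4 | 48.0% | 60.0% | 72.0% |

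At S = 75% each such event costs 0.75/20 = 3.75 percentage points. Over f = 1 to 4 and the three values of S, the evaluable-only figure is too high by 3 points (60% against 57%) to 18 points (90% against 72%). The factor (N − f)/N applies equally at 24 and 60 months, because early events lower the whole curve.

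**4. Sensitivity to censoring.** Suppose instead that 16 are scanned with 12 event-free at 12 months, and that the 4 − f unscanned patients without an event are censored at first dose. All-treated PFS is then 12/(16 + f): 75.0%, 70.6%, 66.7%, 63.2% and 60.0% for f = 0 to 4. The picture is the same.

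**The case against.** The strongest reply is that the authors meant the sentence for response. The definition it relies on is worded for response and sits under Primary Endpoints. Section 14.3 also describes further evaluable sets parameter by parameter, according to whether a patient has the measurements needed for an interpretable result. A treated patient who dies is interpretable for PFS. This may well be the intent, but the sentence covers all outcome analyses and no set is named for PFS. If response only was meant, the same edit is needed to say so.

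A reader might infer that everyone who dies or progresses clinically before the week-12 scan is excluded. The documents do not support that for progression. The definition asks for one post-baseline assessment at any time; it need not be the week-12 scan or come before the event. Section 5.3 lists MRI at completion of therapy or relapse, Appendix 3 (note 3) calls for it at end of therapy, off study or at progression, and Section 5.4 continues it every 3 months in the first year off therapy. A clinical progressor imaged under these rules stays in. The gap is limited to patients never imaged after baseline, for instance after a very early death, or where imaging was not feasible before follow-up ended. Section 3.5 ends follow-up when new tumor-directed therapy starts.

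Four such events would also be unusual here. Eligibility requires grade 1 or 2 glioma and performance status of at least 50. Section 2.1 cites 69% 5-year EFS with carboplatin and vincristine in NF1, and 96% 2-year PFS with selumetinib. The allowance of four can include patients never dosed, who belong to neither set. These points stand, so 60% is an extreme and not a forecast.

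Finally, PFS is secondary, untested and largely descriptive, and the planned CONSORT diagram would show withdrawals and their reasons. That limits the consequence, but a diagram does not put a missing event into the PFS estimate.

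**Conclusion.** Wrong as written. The closing rule of Section 14.3 conflicts with the full-analysis set defined earlier in the same section. Taken literally, it drops treated patients who have a PFS event and are never imaged after baseline, which can only bias PFS upward.

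The size depends on how many such patients there are, which the documents cannot tell us. With none, this bias is zero. With one among 20 treated and an assumed 75% PFS in the scanned, 12-month PFS is 71% where the evaluable-only analysis reports 75%; with four it is 60%. These are illustrations on assumed rates, with all 20 patients dosed. They do not show that the trial's PFS will be overstated by any given amount. The primary response decision is unaffected.

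A reader might also infer that the responding set has no place in tumor-control analyses. That goes too far: Section 10.5 defines duration of response, for which responders are the natural set. The set is unsuitable for PFS timed from first dose, where it would select on the future more strongly still.

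**What to change.** - Limit the closing sentence of Section 14.3 to response-based endpoints.
- State that PFS at 12, 24 and 60 months uses the full-analysis set (all who received at least one dose), and that events count whether or not a scan was done.
- Censor event-free patients in line with Section 14, at the last follow-up at which they were known to be event-free, or at first dose if there is none.
- Keep the responding set for duration of response only.

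Section 10.5 starts PFS at enrollment and lists fewer events than Section 14. That is a separate inconsistency, conveniently settled in the same edit.

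The cost is wording only: no new data and no extra patients, with N = 16 and the cut-off of 3 unchanged. Response itself should stay on the evaluable set unless its rule is redesigned, because the cut-off does not carry over. With 20 patients, 3 responders would give an exact alpha of 0.0755, and 4 would give 0.0159 with power 0.775.
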